**I. Purpose, Background and Rationale**

**A. Aim and Hypotheses**

1. Use of electronic cigarette (e-cigarette) and heat-not-burn (HNB) products is continuing to proliferate in the US. In fact, e-cigarette use is expected to surpass combustible cigarette smoking rates in the next two years. The US FDA has regulatory authority to set appropriate product standards for e-cigarettes and heat-not-burn products with the goal of maximizing public health. Initial data suggest that these products present reduced harm compared to combustible cigarette smoking, but the comparative abuse liability and interest in use by smokers, particularly as a function of product flavor, remains largely unknown. These questions are critical in helping the FDA impose meaningful and effective regulations on these products. African American (AA) smokers are showing increased interest in these new and emerging products. Research suggests AA smokers take larger puffs and inhale more deeply than whites. Therefore, data are needed to understand if AA smokers will also use e-cigarettes and HNB devices in such a way that could inadvertently increase harm in the long run. Additionally, research is urgently needed to understand whether these products (if shown to be less harmful than cigarettes), would be an acceptable alternative to traditional smoking and how product flavor (tobacco vs. menthol) impacts use patterns and preference. The current study is not a cessation study and does not aim to induce long-term uptake of the study products. The objective of the study is to test the acute pharmacokinetic profile of these products during a 65-minute use period with each product across three to four study visits.

2. Aim 1: Understand the abuse liability of heat-not-burn devices, e-cigarettes, and combustible cigarettes in terms of nicotine delivery, puff patterns (topography), and reductions in nicotine withdrawal/craving. H1: Combustible cigarettes will show the fastest and greatest nicotine delivery, followed by e-cigarettes, and heat-not-burn devices. H2: Topography measures will be greatest for cigarettes, followed by e-cigarettes, and heat-not-burn devices. H3: Use of cigarettes will be associated with the greatest reduction in symptoms of nicotine withdrawal and craving.

Aim 2: Examine resultant toxicant exposure of heat-not-burn devices, e-cigarettes, and combustible cigarettes. H1: Exhaled carbon monoxide will be greatest for cigarettes, followed, by heat-not-burn devices and e-cigarettes (no exposure).

**Aim 3:** Understand the comparative acceptability of tobacco and menthol flavored e-cigarettes among menthol cigarette smokers. H1: Menthol cigarette smokers will show increased topography measures when using the menthol (vs. tobacco) flavored e-cigarette. H2: Menthol cigarette smokers will show increased acceptability and more positive subjective effects when using the menthol (vs. tobacco) flavored e-cigarette.

**Exploratory Aim:** Understand differences in abuse liability of e-cigarettes, HNB products, and cigarettes as measured behaviorally in a concurrent choice task.

## **B. Background and Significance**

1. **Study Significance:** Electronic cigarettes (e-cigarettes) and heat-not-burn (HNB) devices have been introduced to the US market in the past 15 years. The US Food and Drug Administration (FDA) is tasked with regulating these emerging products in order to maximize public health. To do this, data are needed regarding product effects including abuse liability (nicotine delivery, addiction potential, and reductions in nicotine withdrawal/craving), product demand, and resultant toxicant exposure. Further, research suggests that these products present reduced harm to the user compared to combustible cigarettes. If this is continually shown to be the case, they may be a less harmful alternative to smoking combustible cigarettes. However, it remains unclear whether they are an acceptable alternative to smokers and whether smokers would choose to use them in place of combustible cigarettes, particularly as a function of flavor (menthol vs. tobacco). Moreover, as more smokers transition to these new and emerging products, it is important to understand how underserved populations will use these products. African American (AA) smokers bear a disproportionate burden of smoking-related diseases and represent an understudied population with a propensity to use products in a way that is different compared to the majority population. AA smokers take larger puffs and inhale more intensely on cigarettes than whites. Therefore, data are needed specific to this population to understand how to maximize public health while avoiding harm to underserved populations, such as AA smokers. The long-term goal of this research is to provide data urgently needed by the public health community and policy makers in order to inform regulatory decisions and maximize public health.
2. **Overall Literature Review:** The current study will utilize a nicotine salt-based e-cigarette from JUUL. Research from JUUL shows that it can deliver cigarette-like levels of nicotine to the user. One independent study showed that JUUL delivered a higher and faster boost in nicotine compared to other e-cigarette devices and showed that the boost and rate of nicotine delivery was comparable to smoking one cigarette when used by established e-cigarette users. One recent study reports on nicotine delivery among smokers and indicates that JUUL approached but did not reach cigarette-like levels of nicotine delivery. Unpublished data from our laboratory suggest that some smokers are able to effectively extract nicotine from JUUL while others may necessitate significant practice in order to achieve cigarette-like serum nicotine levels. In regards to HNB, we will be using the IQOS device created by Philip Morris International (PMI). Until recently, the only data on the abuse liability and nicotine delivery of this product were from PMI. To our knowledge, only one recently published independent study has been conducted and showed that while IQOS significantly increased nicotine levels

following the 10-puff PK assessment and ad lib use, it did not reach cigarette-like levels of nicotine delivery. Data from PMI on the pharmacokinetics (PK) of IQOS suggest that the device is capable of delivering cigarette-like levels of nicotine in a regimented PK study as well as when users engage in ad lib smoking. However, we are unaware of any independent studies comparing the IQOS HNB product, popular e-cigarettes, and combustible cigarettes in terms of nicotine deliver, overall abuse liability, or acceptability for substitution. Moreover, we are unaware of any studies examining these concepts in AA smokers, a population particularly vulnerable to tobacco-related harms.

**3. Detailed review:**

**Does brief exposure to e-cigarettes and HNB devices increase risk to smokers?**

- No, there is no evidence to suggest that brief use of e-cigarette or HNB products increases risk to current cigarette smokers above that provided by cigarettes alone. Lab studies of toxin exposure suggest that e-cigarettes incur no greater risk to health than do conventional cigarettes. Indeed, e-cigarettes generally show lower levels of harmful and potentially harmful constituents. The evidence is so strong regarding the reduced harm of e-cigarettes compared to cigarettes, that the National Academies of Sciences, Engineering, and Medicine has concluded that there is “conclusive evidence” that e-cigarettes are associated with reduced harm compared to cigarettes. To date, e-cigarette studies discussing adverse events report mild and tolerable side effects that generally resolved completely over time with continued use; the most predominant of which were mouth/throat irritation, cough, and headache. In four randomized clinical trials, no serious adverse events were reported and the e-cigarette group and the nicotine patch group had comparable levels of adverse events in two studies. The most common were mouth irritation, throat irritation, dry cough and headache. Fewer studies exist on HNB products but those that do, mimic results from studies on e-cigarettes and show that HNB products have lower toxicant levels compared to combustible cigarettes and have lower levels of harmful and potentially harmful constituents. In fact, studies in which smokers are asked to switch to exclusive HNB use, levels of harmful and potentially harmful constituents approach those observed in non-smokers. Similar to the e-cigarette literature, research discussing adverse events with HNB products report no serious adverse events and only mild and tolerable side effects that resolve completely over time. The most common adverse effect was cough.

**What are the effects of dual e-cigarette and conventional cigarette use?**

- Research shows that when smokers begin using e-cigarettes, they reduce the number of cigarettes they smoke per day and show decreases in tobacco-related toxins. In a study conducted by [name] and her team, smokers were asked to completely substitute with e-cigarettes. Approximately 30% were successful in completely substituting. Moreover, those that did not successfully substitute but instead used both cigarettes and e-cigarettes, significantly reduced their cigarettes per day and showed significant reductions in NNAL, a potent lung carcinogen at 6-week follow-up. While those that switch to these products and those that go on to dual use them show reductions in harm, cigarette smokers

continue smoking at their usual rate and show no reductions in toxicant exposure.

**What are the effects of dual HNB and conventional cigarette use?**

- Less information is known regarding dual HNB and conventional cigarette use because the product has only been on the US market for a short time. However, the existing studies show that when randomized to switch completely to HNB products, 64% switched completely. Moreover, users' levels of NNAL dropped significantly from baseline to follow-up and were significantly lower than NNAL levels in the traditional cigarette group at follow-up. While our study is not a switching or cessation trial, these data suggest that brief use of HNB devices by current smoker will not increase their harm. It is also unlikely that they will become dual users of HNB products as this has not been documented in the literature.

**Does use of e-cigarettes and HNB devices increase conventional cigarette smoking?**

- No, e-cigarette and HNB devices do not increase conventional cigarette smoking. As mentioned above, studies conducted by our team show that when provided an e-cigarette, users reduce their cigarette smoking. While the HNB literature remains in its infancy, no studies suggest that brief exposure to HNB products increase cigarette smoking.

**Is the proposed pharmacokinetic evaluation method common?**

- Yes, this method of evaluation is the gold standard for evaluating nicotine delivery and abuse liability. In addition, studies on relatively newer products almost always recruit smokers because cigarette smoking is the most harmful form of tobacco use in the world. Therefore, it is generally agreed that inviting smokers to use a product with potentially reduced harm for a brief period of time incurs no elevated risk to the participant. To date, this method has been successfully applied to assess e-cigarettes, HNB products, and waterpipes. In fact, a recent publication mimicked this study almost exactly but with white smokers and was published in the highest impact journal in the field of tobacco regulatory science. Researchers on this team have been PI and co-I on five such pharmacokinetic studies.

**C. Rationale**

1. Industry-funded studies suggest that HNB devices and popular e-cigarettes can deliver cigarette-like levels of nicotine and therefore have comparable abuse liability profiles to combustible cigarettes. If this is the case and research continues to show that these products expose users to less harm compared to traditional cigarettes, they may be an acceptable product for use by current smokers who are unwilling or unable to quite to reduce tobacco-related harm. However, industry-funded studies are open to bias and therefore independent studies are urgently needed to inform appropriate regulations.
2. The current study will provide objective data on the nicotine delivery and overall abuse liability (craving, reductions in nicotine-related withdrawal symptoms), and acceptability of emerging and popular products (HNB and e-cigarettes) among AA smokers, a population particularly vulnerable to tobacco-related harms and who has been underrepresented to date in data aimed at informing regulations to improve public health. Moreover, we will investigate how flavors in e-cigarettes impact product acceptability and abuse liability (i.e., interest in future use, puff patterns/topography, subjective

experience) among menthol cigarette smokers. These data will be used by the FDA to inform appropriate regulation of these products.

3. Tobacco remains the leading cause of preventable death in the US and each year close to half a million people die due to tobacco-related diseases. Therefore, for smokers that are unable or unwilling to quit, products such as e-cigarettes and HNB devices may present less harm and improve public health.

## **II. Research Plan and Design**

**A. Study Objectives:** The objective of this study is to understand the abuse liability and resultant toxicant exposure of new and emerging tobacco products in comparison to smokers' usual brand cigarette and to further understand how flavors in e-cigarette products impact abuse liability among menthol cigarette smokers. The current study is not a cessation study and does not aim to induce long-term uptake of the study products. The objective of the study is to test the acute pharmacokinetic profile and acceptability of these products during a 65-minute use period with each product across three to four study visits. African American and white smokers (N = 20) will be recruited and complete three to four in-laboratory sessions in a randomized crossover design.

**B. Study Type and Design:** The proposed study is a randomized crossover trial. Current smokers will be randomized to session order and complete a standardized 10-puff bout (5 minutes) followed by a 60-minute ad libitum session with each product (usual brand cigarette, e-cigarette, heat-not-burn). Throughout each visit, blood will be collected for nicotine analysis via an IV catheter placed in the patient's arm. Blood samples will be aliquoted into two separate vials. One will be analyzed for the current study and one will be placed in a biospecimen repository if participant provides consent for biorepository. Puff topography will be collected passively throughout the session to measure puffing patterns. Participants will complete self-report measures of nicotine withdrawal and craving. Finally, breath samples will be collected to measure changes in exhaled carbon monoxide, a potent lung toxicant, pre- and post-product use. At the final visit, participants will complete a behavioral economics concurrent choice task (see below for description) to behaviorally measure their decisions regarding use of e-cigarettes or HNB products in place of cigarettes. Finally, participants will be contacted by phone 6 months following the conclusion of visit 3 (or study discontinuation) to complete a phone survey. The objective of this survey is to assess for ongoing use of study products and is part of safety monitoring. We have no hypotheses related to the follow-up.

Participants who report typically smoking menthol cigarettes will be invited to complete a fourth session. Participants will undergo overnight tobacco/nicotine abstinence before the visit (eCO2≤12ppm). Participants will then be randomized 1:1 to e-cigarette flavor order (tobacco e-cigarette, menthol e-cigarette) and will complete sessions in a counterbalanced fashion to control for order effects. They will complete a 30-minute ad libitum session with the first product, based on randomization, followed by a 1.5-hour standard washout period, followed by a 30-minute ad libitum vaping session with the second product (menthol or tobacco flavor). Throughout each session, puff topography will be measured via a pressure sensor attached to the e-cigarette device. Participants will complete self-report measures of smoking urges and withdrawal symptoms pre- and post-

vaping session. In addition, they will complete measures of subjective vaping experience, perceptions of flavor, product demand, and intentions for future use.

**C. Sample size, statistical methods, and power calculation**

1. 20 eligible AA and white smokers will be randomized. We will use a 1:1 fashion randomization to product order (combustible cigarette, e-cigarette, heat-not-burn device vs. combustible cigarette, heat-not-burn device, e-cigarette). Randomization will be determined by computer-generated random numbers. Randomization assignments will be placed in sealed envelopes with sequential study ID numbers. After baseline data collection has been completed, the research assistant will select the sequential study ID number to determine the randomization assignment
2. No blinding is involved in the first three study visits. For participants who complete the fourth visit (flavor assessment), participants and research assistants that interact with participants will be blind to flavor (double blind design).
3. Due to the pilot nature of the current study, a primary aim of the study is to collect data for power calculations for a fully powered trial. Therefore, formal power calculations were not conducted. ANOVAs will be conducted to detect within-subject differences between products for all outcomes. A Bonferroni correction will be applied to adjust for multiple comparisons. A paired samples t-test will be conducted to detect differences in outcomes in the e-cigarette flavor assessment.

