  - b. **Visit one:** At visit one, participants will be re-screened according to inclusion/exclusion criteria. They will be instructed to remain nicotine abstinent for 12 hours prior to the visit. Participants will complete carbon monoxide (CO) measurement to confirm abstinence ( $CO \leq 12$  ppm). CO is collected by a simple, non-invasive breath test that involves the participant holding their breath for  $\sim 15$  seconds and then exhaling into a straw connected to the CO monitor. Participants will be provided with an overview of the study, will provide informed consent, and complete baseline self-report measures. Participants will then complete the PK phase of the study. Participants will have an intravenous catheter placed in their arm. They will complete a 10-puff standardized puffing bout followed by a 60-minute ad-lib smoking session with their usual brand cigarette. Specifically, a research assistant with a stopwatch will instruct the participant to take a puff every 30 seconds, resulting in 10 puffs over 5 minutes. Throughout the session, puff topography will be measured via a pressure sensor attached to the device/product. This will not require anything additional of the participant. Blood draws will occur during the 10-puff bout at -5, 5, 7, 15, and at the end of the ad-lib smoking period ( $\sim 60$  minutes after the 10-puff bout). Following the smoking period, the participant will be instructed to make notes regarding their preferences related to the product (e.g., liking, satisfaction, craving, intentions/willingness for future use). Participants will complete self-report measures of nicotine craving and withdrawal at each blood draw during the 10-puff bout and every 10 minutes throughout the ad-lib smoking period. At the end of the session, participants will complete a measure of product liking/evaluation. At the end of visit one, participants will be randomized to product order (e-cigarettes followed by HNB device vs. HNB device followed by e-cigarette). Participants will be shown how to use the device, puff on it, charge it, replace the pod/heat stick. Participants will be compensated \$50 for this visit.

[figure not shown]
addition, participants will be asked to bring an unopened pack of their usual brand cigarettes to this visit. They will be compensated an additional \$6 for this, bringing their total compensation to \$56 for this visit. We anticipate the visit to last no more than 3 hours.

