- c. **Between visits one and two:** Participants will be provided with the product to be used at the next visit (determined by randomization completed at the end of visit one) and asked to take it home for 48 hours (+3 days) and instructed to, at minimum, practice using it 2-3 times per day between visits. However, they will be encouraged to full substitute the study product for their cigarettes to ensure they conduct sufficient practice. They will be provided with e-liquid or heat sticks and the device for practice. Participants will complete and return a practice log at the following visit.
- d. **Visit two:** Aside from the product being used, visit two will closely mirror visit one. Participants will complete baseline self-report measures regarding their practice period (product liking/evaluation and preferences). Participants will again complete CO measurement to confirm tobacco/nicotine abstinence. They will complete a PK and ad-lib session identical to visit one. At the end of the session, they will be oriented to the final device and again instructed to practice with (and attempt to fully substitute) it at home. Participants will be compensated \$75 for this visit. We anticipate the visit to last no more than 2.5 hours.
- e. **Between visits two and three:** Participants will be provided with the product to be used at the next visit (determined by randomization completed at the end of visit one) and asked to take it home for 48 hours (+3 days) and instructed to, at minimum, practice using it 2-3 times per day between visits. However, they will be encouraged to full substitute the study product for their cigarettes to ensure they conduct sufficient practice. They will be provided with e-liquid or heat sticks and the device for practice. Participants will complete and return a practice log at the following visit.

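### At visits 1-3 the usual-brand cigarette always comes first, so both cigarette-versus-device contrasts are non-randomised and aliased with visit 1, and the plan does not say so

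*Combined protocol and SAP*

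**What the plan says.** Section II.A says that participants will "complete three to four in-laboratory sessions in a randomized crossover design". Section II.B says "Current smokers will be randomized to session order" and then lists all three products, without noting that one has a fixed position.

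Section II.C item 1 gives two sequences in a 1:1 ratio: "combustible cigarette, e-cigarette, heat-not-burn device vs. combustible cigarette, heat-not-burn device, e-cigarette". Section II.E item 2.b places a session at visit 1 "followed by a 60-minute ad-lib smoking session with their usual brand cigarette" for every participant, and adds: "At the end of visit one, participants will be randomized to product order (e-cigarettes followed by HNB device vs. HNB device followed by e-cigarette".

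For the later visits, II.E item 2.d says: "Aside from the product being used, visit two will closely mirror visit one". Before each device visit, participants take the device home, and "they will be encouraged to full substitute the study product for their cigarettes to ensure they conduct sufficient practice".

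The analysis (II.C item 3 and V.A) is a within-subject ANOVA across products with a Bonferroni correction. It names no visit term. The only mention of order effects concerns the visit-4 flavour test, where II.B says that participants will "complete sessions in a counterbalanced fashion to control for order effects".

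**The concern.** Randomisation carried out after the cigarette session cannot protect a comparison that involves that session. Visit 1 differs from visits 2 and 3 in more than the product: it is the first laboratory session and the first catheter, and consent is taken there. Visits 1-3 are also unblinded. Any effect of being at the first visit falls entirely on the cigarette.

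The contrasts affected carry the cigarette part of Aim 1 H1-H3 (nicotine delivery, topography, withdrawal and craving) and of Aim 2 H1 (exhaled CO). Section V.B makes nicotine delivery the primary endpoint. Section II.C item 3 also makes these data an input to the power calculation of a later trial. A visit-1 effect would pass into that calculation and, unlike sampling noise, would not shrink as the sample grows.

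A separate feature is that home practice precedes the device sessions only. The comparison is therefore of a practised device with the usual cigarette, whatever the order.

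**Working it through.** **Inputs.** From II.C: 20 participants, two sequences (C-E-H and C-H-E, where C is the cigarette, E the e-cigarette and H the HNB device), 1:1 allocation, and an ANOVA on product. Assumed: exactly 10 per sequence. The plan gives no power calculation, alpha, SD or visit effect, so it has no figure of its own to reproduce.

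**1. What can be estimated.** Take the model outcome = subject + visit + product. It has 20 subject columns, 2 visit contrasts and 2 product contrasts, 24 in all. The rank is 23. One dimension is lost because *product is cigarette* and *visit is 1* pick out the same rows. E minus C and H minus C are not estimable. E minus H is estimable, with variance 2σ²/20 = 0.10σ².

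**2. Where a visit effect goes in the product-only ANOVA.** Let v1, v2 and v3 be the visit effects. At 10:10:
- cigarette mean = c + v1
- e-cigarette mean = e + (v2 + v3)/2
- HNB mean = h + (v2 + v3)/2

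So C minus E = (c − e) + [v1 − (v2 + v3)/2], and C minus H has the same bracket. E minus H has no visit term. A visit-1 shift of +1 unit with no product effect gives +1 in both cigarette-minus-device contrasts and 0 in E minus H. A drift of 0, 1, 2 over the visits gives 0 − 1.5 = −1.5, −1.5 and 0.

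**3. What a pre-use reading removes.** Suppose visit 1 adds *a* to the pre-use reading and *a + b* to the post-use reading. The change score keeps only *b*, so a pure level shift (*b* = 0) cancels. This is available for:
- nicotine (draw before the puffing bout);
- craving and withdrawal (completed at each draw in that bout, II.E item 2.b);
- CO (before and after use, II.B).

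Ad-lib topography and end-of-session liking have no pre-use value to subtract. The analysis text does not say that change scores will be used.

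**4. Illustration of size, under assumed inputs.** Paired t-test, n = 20, df = 19, no product effect, shift of δ SDs of the paired difference, two-sided alpha 0.05/3 = 0.0167 (three product pairs). The critical value is 2.625 and the noncentrality is δ√20.

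| δ | δ√20 | Probability of a false difference |
|---|---|---|
| 0.2 | 0.894 | 0.059 |
| 0.3 | 1.342 | 0.125 |
| 0.5 | 2.236 | 0.373 |

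The rates are the same for either sign of the shift.

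**5. Cost of a visit term in E versus H.** The expected 95% half-width, in within-subject SDs, is t × √0.10 × E(s)/σ.
- Product only, df 19, no visit shift: 2.093 × 0.3162 × 0.9869 = 0.653.
- With visit, df 18: 2.101 × 0.3162 × 0.9862 = 0.655, about 0.3% wider.
- Product only, with an assumed visit 2-versus-3 shift of 0.5 within-subject SD: 0.695. The model with visit is then about 6% narrower (0.655/0.695 = 0.943).

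**6. Carryover in E versus H.** Let kE and kH be what each device carries into visit 3. With visit in the model, the estimate is half the sum of (E2 − H3) and (E3 − H2), where the number is the visit. That equals (e − h) + (kH − kE)/2, so half of any difference in carryover enters the contrast.

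**The case against.** The strongest reply is that the order is disclosed and may be deliberate. Sections II.C and II.E both set it out, and the II.B statement about session order is true of the two sequences listed. Cigarette-first also records usual smoking before anyone has been encouraged to replace cigarettes with a device; a cigarette session after a device could carry that substitution over. The documents give no rationale, so this benefit is inferred from the procedures, but it is plausible. It supports keeping the order. It does not make the cigarette contrasts randomised, and II.A and II.B leave a reader thinking that they are.

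A second reply is that much is standardised: 12-hour abstinence, a CO check, paced puffs and a pre-use reading for several outcomes. This stands in part. It limits the routes by which visit 1 could matter, and change scores remove a level shift. It leaves a visit-1 difference in the response to use, and it helps less for ad-lib topography and liking.

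A third reply is that this is a 20-person pilot. That explains the absence of a power calculation. It has no bearing on the aliasing, which no sample size with this order would reveal or resolve.

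A reader might also infer that the cigarette results are known to be biased, or that the trial is not randomised at all. The documents support neither. They give no evidence of a visit-1 effect, and the device order and the visit-4 flavour order are both randomised.

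**Conclusion.** The concern holds as a matter of design and labelling. For visits 1-3, randomisation covers e-cigarette versus HNB only. Both cigarette contrasts are within-subject comparisons with a fixed first-visit reference, fully aliased with visit 1. In the planned ANOVA at 10:10, the gap between the visit-1 effect and the mean of the visit-2 and visit-3 effects enters them one for one. The aliasing is algebra and needs no assumed effect size.

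The size and direction of any bias are unknown; it could create, enlarge or hide a difference. The 6%, 12.5% and 37% rates rest on assumed shifts and an assumed alpha and show sensitivity only. For outcomes with a pre-use reading they apply, after taking change scores, only to a shift in the response to use. The point should be fixed because it touches the primary endpoint and the input to the later trial, and because the correction is cheap. It is not grounds for changing the session order.

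**What to change.** 1. In II.A, II.B and V.A, state for visits 1-3 that every participant completes the cigarette session first and that only the e-cigarette/HNB order at visits 2 and 3 is randomised 1:1. Leave the visit-4 description as it is.
2. Analyse nicotine, craving, withdrawal and CO as change from the pre-use reading. Report all cigarette contrasts with confidence intervals, described as comparisons of a practised device with a fixed-order, non-randomised first-visit reference. Say that the intervals do not allow for a visit-1 effect. Carry this description to Aim 1 H1-H3, Aim 2 H1 and any use of the estimates to power the later trial.
3. Analyse e-cigarette versus HNB within subject with a visit term (2 versus 3), and state the assumption that the first take-home device has no differential carryover. With 20 participants this can be stated but not well tested.

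**Cost.** Wording, the change-score definition and one model term. Visits, randomisation and data collection are unchanged. The device comparison goes from 19 to 18 degrees of freedom, with an expected 95% interval about 0.3% wider if there is no visit shift and about 6% narrower at an assumed shift of 0.5 within-subject SD. The claims about cigarettes become more modest.
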